Many of the subjects showed a pre-existing immune response to target antigens at baseline (baseline immune response to the respective TAA). Overall, 21 (84%) of 25 evaluable subjects fulfilled the criteria for humoral and / or cellular immune responders. Ten (40%) subjects fulfilled criteria for cellular immune responders to any of the CV9202 encoded antigens at any post-baseline assessments based on either IFN-γ ELISpot or flow cytometry-based intracellular cytokine staining (ICS). The frequency of CD4 (measured by ICS) immune responders to any CV9202 encoded antigen was slightly higher compared to that of CD8 responders (measured by ICS) at any post-baseline assessment time-point (28.0% / 7 subjects vs. 16.0% / 4 subjects, respectively). All 25 subjects in the evaluable population were positive for IgM and IgG against any of the CV9202 encoded antigens at baseline. Twenty (80%) subjects had a humoral immune response post-baseline (i.e. IgG or IgM against any of the CV9202 encoded antigens at any post-baseline time point) and were rated as humoral immune responder after applying responder criteria. The majority of subjects (19 [76.0%]) were responders for IgG at any post-baseline time point, whereas only few subjects (7 [28.0%]) were positive for IgM at post-baseline time points. A total of 13 (52%) subjects were multiple responders, i.e. 9 subjects in stratum 1 and 4 subjects in stratum 2. Overall, only a limited number of the performed post-baseline cellular immunomonitoring assays fulfilled “immune responder” criteria for the individual assay outcome, and among those, persistence over both post-baseline time points was not common.

The tolerability profile of BI 1361849 appeared very similar to that of other RActive® vaccines. All subjects reported at least one AE and 25 (96.2%) subjects reported BI 1361849 related AEs. Eleven (42.3%) subjects reported serious adverse events (SAEs), none of which were considered BI 1361849 related. Treatment-emergent AEs by maximum CTCAE grade were Grade 1 (4 [15.4%] subjects), Grade 2 (7 [26.8%] subjects), Grade 3 (13 [50.0%] subjects), and Grade 4 (2 [7.7%] subjects). The two Grade 4 events, neutrophil count decreased, were not considered related to BI 1361849. With very few exceptions, BI 1361849-related AEs were of Grade 1 and Grade 2. Three of the Grade 3 AEs (one subject with pyrexia and 2 subjects with fatigue) were considered related to BI 1361849. No drug-related SAE has been reported in the trial. A low number of subjects experienced nausea/emesis considered related to BI 1361849 in the trial.

The most frequent AEs reported were erythema at the injection site and pyrexia, mostly being reported as vaccine-related but of grade 1 only. Flu-like symptoms potentially represent a pharmacodynamic effect (mimicking of a viral infection, stimulation of the innate immune system via TLRs 7 and 8 due to the RNA-related properties). None of the findings, including e.g. cardiorespiratory or vascular AEs, suggest the occurrence of an uncontrolled release of cytokines or the emergence of autoimmune disorders. This is in line with experience with other vaccines directed against BI 1361849 encoded antigens, which suggests that autoimmune disorders are not commonly observed with such treatment.

## 2 Study Rationale

As described in Section 1.1, checkpoint inhibitors, particularly PD-1/PD-L1 antibodies, have been shown to be effective in the treatment of NSCLC. Checkpoint inhibitors are also associated with minimal toxicities compared with chemotherapy or targeted therapies and function quite distinctly from other therapies. Therefore, the potential for effective and safe combination with existing therapies is significant.

Vaccine therapies stimulate the immune system to attack cancer cells (“active immunotherapy”), as opposed to blocking immune inhibition in the TME by checkpoint inhibitors (“passive immunotherapy”). Randomized vaccine studies in NSCLC have shown benefit in some subgroups. Tecemotide (Stimuvax®) demonstrated overall survival (OS) benefit over placebo in a subgroup of stage III subjects who received concurrent chemotherapy and radiation prior to vaccine, and belagenpumatucel-L (Lucanix®) demonstrated OS benefit in squamous cell carcinoma subjects who were randomized within 12 weeks of completion of prior treatment and in those who had received prior radiation.(22, 23) However, checkpoint mechanisms limit the effectiveness of vaccines at the TME, which may explain why more global long-term benefit from vaccines has not been realized. Therefore, combining “passive immunotherapy” with “active immunotherapy” may overcome some of limitations of vaccine therapy alone. In an animal model of RNActive® vaccination using ovalbumin (OVA) as model cancer antigen stably transfected into E.G7 tumor cells, the combination of the vaccine and a PD-1 inhibitor was more effective than either medication alone. Similar results were also obtained for the combination of the RNActive® vaccine and a CTLA-4 inhibitor. Combination of the PD-1 inhibitor and OVA-RNActive® resulted in complete tumor responses in a part of the treated mice, who were also protected against subsequent rechallenge with the OVA-negative parent tumor cell line.(24)

### 2.1 BI 1361849 Dose

The BI 1361849 drug product is a vaccine comprising six drug product components (F2408, F2409, F2410, F2624, F2625, and F2626), which are provided and administered separately. The recommended dose per antigen constituent is 320 µg (160 µg x 2), for a total of 1920 µg (320 µg x 6 constituents).

BI 1361849 may also be administered by a needle-free device, the PharmaJet Tropis® device. See Section 1.2.3 for additional details.

Due to the filling volume of 100 µL, the device allows for administration of half the previously established doses, i.e., 160 µg instead of 320 µg per antigen when using the same manner of administration of two inoculations per antigen and vaccination time point. Advantages include improved patient convenience, handling safety, ease, and reliability of intradermal administration. Preclinical data showed that using a needle-free device such as the PharmaJet Tropis® device, the efficiency of delivery increases and protein production is higher even at half or a quarter of the administered dose, hence lower doses can be used. Clinical data from a Phase 2 trial, CV-9104-007, suggests that administration of half the dose by the PharmaJet Tropis® device results in at least similar immunogenicity compared to needle administration of the full dose.

For this study, the Pharmajet Tropis® device will be used for the administration of the BI 1361849 components. Allowing for a filling volume of 100 µL (80 µg) and 2 administrations per component, the recommended dose per each of the 6 antigen components will be 160 µg (2 x 80 µg), for a total of 960 µg (12 administrations).

## 2.2 Durvalumab and Tremelimumab Dose

Currently, fixed dosing is recommended for durvalumab and tremelimumab with the dose and schedule of 1500 mg durvalumab Q4W and 75 mg tremelimumab Q4W for subjects > 30 kg.

A population PK model was developed for durvalumab using monotherapy data from a Phase 1 study (*Study 1108; N=292; doses= 0.1 to 10 mg/kg Q2W or 15 mg/kg Q3W; solid tumors*). Population PK analysis indicated only minor impact of body weight on PK of durvalumab (coefficient of  $\leq 0.5$ ). The impact of body weight-based (10 mg/kg Q2W) and fixed dosing (750 mg Q2W) of durvalumab was evaluated by comparing predicted steady state PK concentrations (5th, median and 95th percentiles) using the population PK model. A fixed dose of 750 mg was selected to approximate 10 mg/kg (based on median body weight of approximately 75 kg). A total of 1000 patients were simulated using body weight distribution of 40–120 kg. Simulation results demonstrate that body weight-based and fixed dosing regimens yield similar median steady state PK concentrations with slightly less overall between-subject variability with fixed dosing regimen.

Similarly, a population PK model was developed for tremelimumab using data from Phase 1 through Phase 3 (*N=654; doses= 0.01 to 15 mg/kg Q4W or Q90D; metastatic melanoma*). Population PK model indicated minor impact of body weight on PK of tremelimumab (coefficient of  $\leq 0.5$ ). The weight-based (1 mg/kg Q4W) and fixed dosing (75 mg/kg Q4W; based on median body weight of approximately 75 kg) regimens were compared using predicted PK concentrations (5th, median and 95th percentiles) using population PK model in a simulated population of 1000 patients with body weight distribution of 40 to 120 kg. Similar to durvalumab, simulations indicated that both body weight-based and fixed dosing regimens of tremelimumab yield similar median steady state PK concentrations with slightly less between-subject variability with fixed dosing regimen.

Similar findings have been reported by others. Wang and colleagues investigated 12 monoclonal antibodies and found that fixed and body size-based dosing perform similarly, with fixed dosing being better for 7 of 12 antibodies. In addition, Zhang et al. investigated 18 therapeutic proteins and peptides and showed that fixed dosing performed better for 12 of 18 in terms of reducing the between-subject variability in pharmacokinetic/pharmacodynamics parameters.

A fixed dosing approach is preferred by the prescribing community due to ease of use and reduced dosing errors. Given expectations of similar pharmacokinetic exposure and variability, we considered it feasible to switch to fixed dosing regimens. Based on average body weight of 75 kg, a fixed dose of 1500 mg Q4W durvalumab (equivalent to 20 mg/kg Q4W) and a fixed dose of 75 mg Q4W tremelimumab (equivalent to 1 mg/kg Q4W) are included in the current study.

The 1500 mg Q4W dosing of durvalumab is recommended only for subjects with > 30kg body weight in order to limit endotoxin exposure. Subjects with a body weight  $\leq 30$  kg are not eligible for enrollment in the current study. See Section 3.1.7.1 for additional details regarding the dose

de-escalation cohort for durvalumab and for durvalumab and tremelimumab dose requirements for instances when a subject's body weight drops to  $\leq 30$  kg while on the study.

### 3 Experimental Plan

#### 3.1 Study Design

This is an open-label multicenter Phase 1/2 study to evaluate the safety and preliminary efficacy of the addition of a vaccine therapy to 1 or 2 checkpoint inhibitors for NSCLC:

- **Arm A:** mRNA Vaccine [BI 1361849] + anti-PD-L1 [durvalumab]
- **Arm B:** mRNA Vaccine [BI 1361849] + anti-PD-L1 [durvalumab] + anti-CTLA-4 [tremelimumab]

For each arm of the study, there is a **dose evaluation phase** in which the Recommended Combination Dose (RCD) is determined according to a standard 3 + 3 design. The **dose evaluation phase** is followed by an **expansion phase**, in which the cohort at the RCD for each arm is expanded to 20 subjects (inclusive of the subjects from the dose evaluation cohort).

[figure not shown]
NOTE: The BI 1361849 drug product is a vaccine comprising six drug product components (F2408, F2409, F2410, F2624, F2625, and F2626), which are provided and administered separately. See Section 6.3 for additional details.

##### 3.1.1 Study Phase

Phase 1/2

##### 3.1.2 Enrollment/Randomization

Enrollment will start in the Arm A dose evaluation cohorts in a sequential fashion. After the RCD is determined for Arm A, enrollment will start for the dose evaluation of Arm B (see Section 3.1.7.1) and for the Arm A Expansion Cohort (see Figure 1), whereby no randomizations will be performed. Any new subject will be assigned to the Arm B dose evaluation cohort, unless no slot is available, in which case the subject will be assigned to the Arm A Expansion Cohort. After the dose evaluation and safety review for Arm B is complete, enrollment into the Arm B Expansion Cohort will be prioritized over Arm A (see Figure 1).

**Figure 1. Enrollment Schema for Arms A and B**

\* After the dose evaluation and safety review for Arm B is complete, enrollment into the Arm B Expansion Cohort will be prioritized over Arm A.

### 3.1.3 Blinding/Unblinding

This is an open-label study.

### 3.1.4 Subject Population

Subjects with histologically confirmed metastatic NSCLC. For subjects with known EGFR or ALK/ROS-1 mutations, prior therapy must have included an EGFR tyrosine kinase inhibitor or ALK/ROS-1 inhibitor, respectively. Subjects may have had 1 prior line of anti-PD-1/PD-L1 therapy and must not have had progression at or before 12 weeks after start of treatment. Details on subject eligibility are found in Section 5.

### 3.1.5 Number of Sites/Subjects

Up to 8 sites in the US, with a total of up to 56 subjects.

### 3.1.6 Sample Size Considerations

The *dose evaluation phase* will utilize a standard 3 + 3 design for Arms A and B, which will result in the enrollment of 6 to 18 subjects.

In the *expansion phase*, 20 subjects per arm are thought to provide sufficient data to adequately identify essential safety and preliminary efficacy signals. Therefore, up to 14 additional subjects will be added to the 6 subjects treated at the RCD in each arm (A and B).

The sample size n=20 for the expansion phase is deemed to provide sufficient precision for the estimation of incidence of adverse events. The Clopper Pearson confidence intervals (CI) for incidence of adverse events based on a sample size of 20 subjects are provided below:

Number of Subjects with Event	Incidence	95% Confidence Interval (Clopper Pearson)
1/20	0.05	(0.00127, 0.24873)
2/20	0.10	(0.01235, 0.31698)
3/20	0.15	(0.03207, 0.37893)
4/20	0.20	(0.05733, 0.43661)
5/20	0.25	(0.08657, 0.49105)
6/20	0.30	(0.11893, 0.54279)
7/20	0.35	(0.15391, 0.59219)
8/20	0.40	(0.19119, 0.63946)
9/20	0.45	(0.23058, 0.68472)
10/20	0.50	(0.27196, 0.72804)
11/20	0.55	(0.31528, 0.76942)
12/20	0.60	(0.36054, 0.80881)
13/20	0.65	(0.40781, 0.84609)
14/20	0.70	(0.45721, 0.88107)
15/20	0.75	(0.50895, 0.91343)
16/20	0.80	(0.56339, 0.94267)
17/20	0.85	(0.62107, 0.96793)
18/20	0.90	(0.68302, 0.98765)

CONFIDENTIAL

Number of Subjects with Event 19/20	Incidence 0.95	95% Confidence Interval (Clopper Pearson) (0.75127, 0.99873)
---	--------------------------	--

### 3.1.7 Treatment Arms and Treatment Schema

Study drug will be administered over 12 cycles with a cycle length of 28 days. The study drugs used in this study will be administered per cycle as shown below:

**Note: the dosing intervals for BI 1361849 intervals increase over time**

Cycle (28d)	Cycle Day	Arm A Dosing Schedule		Arm B Dosing Schedule		
		BI 1361849 (12 x i.d. each)	Durvalumab (i.v.)	BI 1361849 (12 x i.d. each)	Durvalumab (i.v.)	Tremelimumab* (i.v.)
1	1	X	X	X	X	X
	8	X		X		
	15	X		X		
2	1	X	X	X	X	X
	15	X		X		
3	1	X	X	X	X	X
	15	X		X		
4	1	X	X	X	X	X
5	1	X	X	X	X	
6	1	X	X	X	X	
7	1		X		X	
	15	X		X		
8	1		X		X	
9	1	X	X	X	X	
10	1		X		X	
	15	X		X		
11	1		X		X	
12	1	X	X	X	X	X

i.d. = intradermal; i.v. = intravenous

#### 3.1.7.1 Dose Evaluation Phase

Each subject enrolled in the dose evaluation cohorts of the study will be evaluated for dose-limiting toxicities (DLTs), as defined in Section 3.1.9. Dose de-escalation and evaluation of RCD will be performed based on the available dose levels (see table below) and the respective rules for a standard 3 + 3 study design (see Schema below).

For Arm A, the RCD of BI 1361849 + durvalumab is determined. The starting dose of durvalumab is 1500 mg with possible de-escalation to 750 mg; the dose for BI 1361849 remains constant. For Arm B, the RCD of BI 1361849 + durvalumab from Arm A with the addition of tremelimumab 75 mg is evaluated. There is no dose escalation/de-escalation for Arm B; if there is unacceptable toxicity in Arm B, the arm will be discontinued.

Dose Level Table for Evaluation Phase						
Dose Level	Arm A		Dose Level	Arm B*		
	BI 1361849	Durvalumab		BI 1361849	Durvalumab	Tremelimumab
-1	12 x 80 µg**	750 mg				
Starting	12 x 80 µg**	1500 mg	Starting	12 x 80 µg**	RCD from Arm A	75 mg

[figure not shown]
\*If there is unacceptable toxicity in Arm B, dosing will continue at RCD from Arm A, without tremelimumab.

\*\*BI 1361849 is a vaccine comprising six drug product components (F2408, F2409, F2410, F2624, F2625, and F2626), which are provided and administered separately; each component is administered twice, thus there are 12 administrations of 100 µL (80 µg) each.

**NOTE 1:** The Pharmajet Tropis® device will be used for the administration of the BI 1361849 components. Allowing for a filling volume of 100 µL (80 µg) and 2 administrations per component, the recommended dose per each of the 6 antigen components will be 160 µg (2 x 80 µg), for a total of 960 µg (12 administrations). See Section 6.3.3 for details on the administration of BI 1361849.

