**Figure 2. Dose Escalation and De-Escalation Schema**

Per Figure 2, the RCD for Arm A and Arm B is defined as the highest dose level at which no more than 1 of 6 subjects (i.e., < 33%) experience DLTs. The RCD cannot be determined if none of the predefined dose level cohorts fulfill that criterion. In such case, the arm will be discontinued without an expansion phase.

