  - Total bilirubin  $\leq 5$  times ULN that downgrades to Grade  $\leq 2$  ( $\leq 3$  times ULN) within 7 days after onset, whereby maximal supportive care, including systemic corticosteroids, is permitted.
  - Grade  $\geq 3$  neutropenia that (1) is not associated with fever or systemic infection, (2) does not require medical intervention, and (3) improves to Grade 2 within 7 days.
  - Grade 3 and 4 lymphopenia.
  - Grade 3 thrombocytopenia that (1) is not associated with clinically significant bleeding, (2) does not require medical intervention, and (3) improves to Grade 2 within 7 days.
  - Isolated Grade 3 electrolyte abnormalities that are not associated with clinical signs or symptoms and are reversed with appropriate maximal medical intervention within 3 days.
  - Any pre-existing laboratory abnormality that deteriorates to Grade 3/4, but where the increment of deterioration is considered not clinically significant by both investigator and sponsor.
  - Grade 3 or 4 asymptomatic increases in amylase or lipase levels for which appropriate evaluation shows no clinical evidence of pancreatitis.

Immune-related AEs (irAEs) are defined as AEs of immune nature (i.e., inflammatory) in the absence of a clear alternative etiology. In the absence of clinical abnormality, repeat laboratory testing will be conducted to confirm significant laboratory findings prior to designation as a DLT.

While rules for adjudicating DLTs are specified above, an AE that is Grade < 3 or listed as exempt above may also be defined as DLT after consultation with the sponsor and Investigators, based on the emerging safety profiles of durvalumab, tremelimumab, and BI 1361849. Likewise, subjects who become not evaluable for DLT, because they discontinued or interrupted treatment due to toxicities other than DLTs, may be counted as DLT subjects, if the toxicities cannot be managed in accordance with the dosing modifications described in Section 3.1.8.

Subjects who experience a DLT will be discontinued from study treatment and will enter the On Study and Post Study Follow-up (see Section 3.1.16). However, if it is in the best interest of the subject, the Investigator, subject and Sponsor may agree to continue treatment with BI 1361849.

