#### 4.1.2 Subject Evaluation and Statistics

The **Per-Protocol (PP) Population for DLT Assessment** includes:

- All subjects who experience a DLT at any time during the DLT Evaluation Period (as defined in Section 3.1.9)
- All subjects with no DLT who receive at least 75% of the scheduled doses of durvalumab and tremelimumab and at least 4 of the 5 BI 1361849 vaccinations as well as respective safety assessments without major protocol violations during the DLT Evaluation Period (as defined in Section 3.1.9)

Refer to Section 3.1.11 for subject replacement.

CONFIDENTIAL

The **Safety Population** is defined as all subjects who receive at least one dose of any of the study drugs.

In the dose evaluation phase, for the primary endpoint of determining DLTs and the RCD, the analysis of safety and tolerability will be based on the **PP Population for DLT Assessment**.

In both phases (evaluation and expansion), the overall analysis of safety and tolerability will be based on the **Safety Population**.

Appropriate summaries of AEs, SAEs, laboratory data and vital signs data will be presented for the Safety Population overall and by cohort. Adverse events will be coded using the MedDRA dictionary. Incidences of treatment-emergent adverse events (TEAE, those events that started after dosing or worsened in severity after dosing) will be presented overall and by maximum severity and relationship to study drugs.

For each continuous laboratory parameter, results will be categorized as low, normal, or high based on the laboratory normal ranges. Frequencies and percentages will be presented for the shifts in these categories (i.e., low to normal, low to high, high to low, etc.) from baseline to each post-treatment assessment time point. Additionally, for each continuous hematology and chemistry parameter, descriptive statistics will be presented for the changes from baseline to each post-treatment assessment time point. Descriptive statistics will be presented for the changes in vital signs from baseline to each post-treatment assessment time point.

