## 2.2 Study Endpoints

### Primary Endpoints

The primary endpoint of the combination therapy of durvalumab and tremelimumab are:

- Dose- Limiting Toxicities (DLTs). DLTs are defined as any adverse events that are possibly, probably, or definitely related to the administration of durvalumab, tremelimumab, or BI 1361849 components. This applies to Dose Evaluation subjects during the DLT Evaluation period.
- Safety and tolerability evaluated using CTCAE 4.03.
- Recommended Combination Dose (RCD) determined in Dose Evaluation Phase.

The safety endpoints for this study include:

[figure not shown]
- Treatment-emergent adverse events (TEAEs) and serious AEs (SAEs)
- Clinical laboratory tests (hematology and chemistry)
- Vital signs and weight measurements
- ECG
- ECOG performance status evaluation
- Any other medically indicated assessments, including subject interviews
- All safety analyses will be reported separately for Arm A and Arm B

The Clinical efficacy endpoints will be assessed by irRECIST and RECIST 1.1 and will include:

- Objective Response rate (ORR) at 8 and 24 weeks. ORR is defined as the percentage of subjects meeting criteria of Complete Response (CR) or Partial Response (PR) over a period of at least 4 weeks.
- Duration of Response (DoR). DoR is defined as the interval between the date of earliest determination of CR or PR to the date of earliest determination of PD, or to the date of death, if PD does not occur.
- Disease Control rate (DCR). DCR is defined as the percentage of subjects meeting criteria of Stable Disease (SD), PR, or CR over a period of at least 4 weeks.
- Progressive Free Survival (PFS) at 8 and 24 weeks. PFS is defined as the interval between the date of first dose to the date of earliest determination of Progressive Disease

(PD), or to the date of death, if PD does not occur. Week 8 corresponds to Cycle 3 Day 1 and Week 24 corresponds to Cycle 7 Day 1.

- Overall Survival (OS). OS is defined as the interval between the date of first dose until the date of death or the date of last follow-up.
- All efficacy analyses will be reported separately for Arm A and Arm B.

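### The protocol gives two actions for unacceptable Arm B toxicity, and the SAP's by-arm tables would combine two durvalumab dose levels if Arm A is de-escalated

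*Protocol*

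**What the plan says.** **Arm B toxicity.** The body text of Protocol 3.1.7.1 states that "if there is unacceptable toxicity in Arm B, the arm will be discontinued". The footnote to the dose table in the same section states: "If there is unacceptable toxicity in Arm B, dosing will continue at RCD from Arm A, without tremelimumab". The synopsis repeats both. The text under Figure 2 defines the RCD as "the highest dose level at which no more than 1 of 6 subjects (i.e., < 33%) experience DLTs" and, where no level qualifies, says "the arm will be discontinued without an expansion phase". Protocol 3.1.9 adds: "Subjects who experience a DLT will be discontinued from study treatment". It allows BI 1361849 alone to continue by agreement. SAP 2.3 keeps the discontinuation sentence and omits the footnote.

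**Reporting unit.** Protocol 4.1.2 says that summaries of AEs, SAEs, laboratory data and vital signs "will be presented for the Safety Population overall and by cohort". Protocol 4.2.2 bases the efficacy analyses on the ITT and PP populations within each cohort. SAP 2.2 says: "All safety analyses will be reported separately for Arm A and Arm B". SAP 2.2 and 3.1 set the same rule for efficacy.

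**Arm A dose levels.** Protocol 3.1.7.1 starts durvalumab at 1500 mg and allows de-escalation to 750 mg, so one arm can hold two regimens. Sections 3.1.6 and 3.1.7.2 plan 20 subjects at the RCD in each arm: 6 from dose evaluation plus 14 added.

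**The concern.** Two points meet here, and both matter only if a toxicity rule is triggered.

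First, sites and the safety panel would have two written instructions for the same event. One ends the arm. The other has dosing go on without one drug. A toxicity rule should have a single reading before it is needed, and the analysis needs to know how to present anyone dosed under the footnote.

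Second, the trial's main product is a safety profile, with preliminary efficacy, in 20 subjects at the RCD of each arm. The precision table in Protocol 3.1.6 is built on that n = 20. If the 1500 mg level fails in Arm A, a table whose only column is Arm A no longer estimates that quantity, because it also contains the subjects treated at the rejected level. SAP 1.0 says the SAP outlines its differences from the protocol's analysis methods. This one is not outlined.

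**Working it through.** **Step 1. The Arm B statements side by side.**

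| Source | Action on unacceptable Arm B toxicity |
|---|---|
| Synopsis and Protocol 3.1.7.1, body text | Arm discontinued |
| Synopsis and Protocol 3.1.7.1, dose-table footnote | Dosing goes on, tremelimumab dropped |
| Protocol 3.1.7.1, text under Figure 2 | No RCD: arm discontinued, no expansion |
| Protocol 3.1.9 | A subject with a DLT leaves study treatment (BI 1361849 alone may continue by agreement) |
| SAP 2.3 | Arm discontinued |

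The trigger is the same in the first two rows and the actions differ. The visible text does not limit the footnote to ongoing subjects without a DLT, and the SAP does not say how subjects dosed under it are to be presented.

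**Step 2. The plan's own precision figure.** The inputs are n = 20 and the 95% Clopper-Pearson method (Protocol 3.1.6). The lower limit is the 0.025 quantile of Beta(x, n − x + 1). The upper limit is the 0.975 quantile of Beta(x + 1, n − x). For x = 4 this gives 0.05733 to 0.43661, as printed. All 19 rows reproduce, with a largest difference of 0.000005. No stated figure is wrong.

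**Step 3. What a by-arm column does after de-escalation in Arm A.** The inputs are 20 subjects at 750 mg and up to 6 DLT-evaluable subjects at 1500 mg. Replaced subjects who had been dosed would add to the 6.

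- Share of the column at the rejected level: 6/26 = 23%.
- Pooled rate = (20 × p_RCD + 6 × p_1500)/26, so the shift from the RCD rate is (6/26) × (p_1500 − p_RCD).
- Assumed counts of 4/20 and 2/6: pooled (4 + 2)/(20 + 6) = 6/26 = 23.1% (95% CI 9.0 to 43.6%). Kept apart, they are 4/20 = 20.0% (5.7 to 43.7%) and 2/6 = 33.3% (4.3 to 77.7%). The shift is 3.1 percentage points.
- Assumed counts of 2/20 and 2/6: pooled 4/26 = 15.4% against 10.0%. The shift is 5.4 points.

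The documents give no event counts. These two cases only show that the shift depends on the gap between the dose levels.

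**Step 4. How likely a failed level is.** The documents give no DLT rate, so this is a range over an assumed true rate p. For a standard 3 + 3, P(fail) = P(≥2 of 3) + P(1 of 3) × P(≥1 of the next 3). For p = 0.20 this is 0.104 + 0.384 × 0.488 = 0.291.

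| Assumed DLT rate | Standard 3 + 3 | If 6 are always treated, P(≥2 of 6) |
|---|---|---|
| 0.10 | 9% | 11% |
| 0.20 | 29% | 34% |
| 0.30 | 51% | 58% |

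**The case against.** **The two Arm B statements can be read together.** One speaks of the arm and the other of dosing. Closing the arm without expansion, while treated subjects without a DLT continue without tremelimumab, would satisfy both. The version history in Protocol 8.1 records the discontinuation sentence as a clarification made in Amendment 2, which suggests that the sponsor saw no conflict. The figures are not visible to this review, so a schema might show the intended path. All of this is fair, and it makes the problem one of unstated scope. It does not remove the problem, because no visible text states that reading.

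**The arm-versus-cohort contrast is not clean.** SAP 9.2 asks for some laboratory summaries by arm and cohort. SAP 9.5 and 9.7 mention cohorts as well. Protocol 4.2.2 summarises tumor response by arm. Separating the arms does not forbid dose-level columns, and SAP 13.0 leaves layout to mock shells. SAP 8.0 counts Arm A subjects with durvalumab de-escalated, and SAP 9.1.1 lists all AEs and DLTs. This stands, but a count and a listing do not split an AE or efficacy table. Nor does the word cohort settle it: SAP 2.1 uses it for the two expansion arms, while Protocol 3.1.7.1 uses it for dose levels.

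**Stronger readings a reader might infer, which the documents do not support.**

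- That Arm B subjects dosed without tremelimumab would move into Arm A. Assignment is made when a new subject enters (Protocol 3.1.2, SAP 2.4), and nothing provides for reassignment.
- That the footnote makes Arm B exposure mixed in general. The flowchart and SAP Appendix B schedule no tremelimumab after Cycle 4 (the table in Protocol 3.1.7 marks one more dose at Cycle 12). Time off tremelimumab is therefore part of the design, and SAP 8.0 already summarises the number of doses, duration and total dose.
- That pooling overstates the RCD event rate by half. That follows only from the assumed 2/20 and 2/6. The resulting 15.4% lies inside the protocol's own interval for 2/20, 1.2 to 31.7%. In both worked examples pooling raises the apparent RCD rate, so it would not conceal toxicity there.

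**RCD selection is unaffected.** DLTs are judged within the dose-level cohort in the DLT per-protocol population, before any by-arm table is made.

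**Conclusion.** The concern holds in two limited parts.

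The wording conflict on Arm B toxicity is certain. It appears in both the synopsis and Protocol 3.1.7.1, and SAP 2.3 reflects only one side of it. This review takes no view on which action is right.

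The reporting mismatch between SAP 2.2 and 3.1 and Protocol 4.1.2 and 4.2.2 is also there in the text, but it has an effect only under a condition. If Arm A is de-escalated and the tables are built by arm alone, up to 6 of 26 subjects in the column come from the rejected level. The shift is then 6/26 of the difference between the two rates, 3.1 points with the assumed 4/20 and 2/6. That is small beside the width of an interval at n = 20. The reason to act is that the column would no longer describe the planned RCD cohort.

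The documents do not report that either toxicity rule was triggered. The failure probabilities rest on assumed DLT rates and show only that the case is not remote. The point is minor: worth a clarification, and no threat to the design.

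**What to change.** 1. **Protocol synopsis and 3.1.7.1:** reconcile the body text with the footnote, and state whether the footnote covers only ongoing subjects. The sponsor decides the clinical content. Align SAP 2.3 with the result.
2. **SAP 2.2, 3.1, 7 and 9:** define the reporting unit as arm and dose-level cohort, with the RCD cohort (n = 20) as its own column. Define cohort once and use it in that sense throughout.
3. **SAP tables and listings:** flag, within Arm B, any subject who continues without tremelimumab because of the toxicity rule. Cohort columns alone would not show this, since such subjects stay in the same cohort.

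The cost is a short protocol clarification, a column definition in the table shells and one flag variable. No further data are needed, and if neither toxicity rule is triggered the outputs stay as they are.
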